8.2 Responsibility for Analyses

The statistical analysis of the data obtained from this study will be the responsibility of the Principal Investigator ([name], HMar) and the biostatistician of the study ([name], HMar).

8.3 Hypotheses

Objectives and hypotheses of the study are stated in Section 3.

8.4 Analysis Endpoints

Key efficacy and safety endpoints that will be evaluated for within- and/or between-tSCS protocols are listed below, followed by the descriptions of the derivations of selected endpoints.

8.4.1. Efficacy Endpoints

Rationale for the key efficacy endpoints is given in Section 4.2.3.1 and an initial description of the efficacy measures is included in Section 7.1.2.2. In general, if a baseline value exists for a particular efficacy measure, then the change from baseline in that value will be evaluated.

Primary Endpoint

Differences in the nine-hole peg test (9-HPT) affected hand in the tSCS treated vs. sham groups by the end of treatment (V3 vs V5)

Secondary Endpoint

1. Percentage of responders: 20% difference on the 9HPTd (minimal clinically important difference (MCID)) from baseline to end of the study
2. Change in the 9HPT dominant and non-dominant hand from baseline to end of the study
3. Change in the Action Research Arm Test (ARAT) from baseline to end of the study
4. Change in the modified Ashworth Scale (mAS) for spasticity assessment from baseline to end of the study
5. Hand strength measured by Grip and Pinch force dynameters (Figure 10)
6. Change in the NeuroQOL Upper Extremity function from baseline to end of the study
7. Change in the Modified Fatigue Impact Scale (MFIS) from baseline to end of the study
8. Change in Global Impression of change (GIC) from baseline to end of the study

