6.0 TRIAL FLOW CHART

Table 2 Trial flow chart

Visit Number	1	2	3-6	7
Visit Title	Screening	Randomization Baseline	Double blinded assessment	OLE

Scheduled Week/Day	Day 0	Day 42	Days 42-61-84	Day 126
Scheduling Window by Days:	±2	±3	±3	±5
Administrative Procedures				
Informed Consent – Subject	X			
Inclusion/Exclusion Criteria	X			
Subject Identification Card	X			
Medical History	X			
Prior Medication Review	X			
Randomization		X		
Monitor Trial Device Compliance		X		
Clinical Procedures/Assessments				
9HPT		X	X	X
ARAT		X	X	X
mAS		X	X	X
NeuroQOL		X	X	X
MFIS		X	X	X
GIC		X	X	X
Safety		X	X	X

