7.1.4 Other Procedures

7.1.4.1 Withdrawal/Discontinuation

When a subject discontinues/withdraws from participation in the trial during visit 2 (before completing the three planned stimulations), all applicable activities scheduled for the end of visit 2, as outlined in Section 6.0 Trial Flow Chart, will be performed at the time of discontinuation. Any adverse events which are present at the time of discontinuation/withdrawal will be followed in accordance with the safety requirements outlined in Section 7.2 - Assessing and Recording Adverse Events

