7.1.5.1.2 Visit 2: Baseline

Patients will be randomized to either treatment or sham stimulation and assigned a code. Before starting stimulation, the researcher will conduct a vital signs and neurological examination. Then, the patient will be subjected to the first tSCS stimulations (a 30 min stimulations).

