7.1.5.1.3 Visit 3-5: Stimulation Visits

At each visit the patient will be reassessed for vital signs. After the completion of each session period. 9HPT will be assessed the last day of stimulation for each session period.

7.1.5.1.2 Visit 13, 14 and 29: end of DBP, onset and end of OLE

During such visits, vital signs, and neurological exam and 9HPT will be conducted.

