7.2.3 Immediate Reporting of Adverse Events

7.2.3.1 Serious Adverse Events

A serious adverse event is any adverse event occurring at any therapeutic regimen or during any use of the product that:

- Results in death;
- Is life threatening;
- Results in persistent or significant disability/incapacity;
- Results in or prolongs an existing inpatient hospitalization;
- Is a congenital anomaly/birth defect;
- Is another important medical event.

Note: In addition to the above criteria, adverse events meeting either of the below criteria, although not serious per ICH definition, are reportable in the same timeframe as SAEs to meet certain local requirements. Therefore, these events are considered serious for collection purposes.

- Is a cancer;
- Is associated with an overdose.

Refer to [Table 3](#) for additional details regarding each of the above criteria.

For the time period beginning when the consent form is signed until treatment, any serious adverse event, or follow up to a serious adverse event, including death due to any cause, that occurs to any subject must be reported within 24 hours for weekly days or 72 days over the weekend if it causes the subject to be excluded from the trial, or is the result of a protocol-specified intervention, including but not limited to washout or discontinuation of usual therapy, diet, sham treatment or a procedure. The 24 hours for the site starts when the site becomes aware of the SAE. SAEs not reported will be considered a major protocol deviation.

For the time beginning at treatment allocation through 14 days following cessation of treatment, any serious adverse event, or follow up to a serious adverse event, including death due to any cause, whether or not related to the product, must be reported within 24 hours either by electronic media or paper. Electronic reporting procedures can be found in the EDC data entry guidelines. Paper reporting procedures can be found in the Investigator Trial File Binder (or equivalent).

Additionally, any serious adverse event, considered by an investigator who is a qualified physician to be related to the product that is brought to the attention of the investigator at any time outside of the time specified in the previous paragraph also must be reported immediately.

All subjects with serious adverse events must be followed up for outcome.

7.2.3.2 . Events of Clinical Interest (during the stimulation visit 2 (in the 1h after each stimulation))

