8.4.2 Safety Endpoints

Presence of serious adverse events (together with items of special attention)

An initial description of the safety measures is included in Sections 7.1.2.1, 7.1.2.2.10 and 7.1.3. Safety and tolerability will be assessed by statistical and clinical review of the following data collected throughout the study: adverse experiences (AEs), and treatment-emergent suicidality. The primary time for safety analyses is Visit 2; Safety endpoints are classified into 2 tiers (see Statistical Methods for Key Safety Analyses in Section 8.1 for Tier definitions).

Tier 1 Safety Endpoints include (the proportion of subjects with):

1. Any AE
2. Any Serious AE
3. Any treatment-Related AE
4. Any Serious and treatment-Related AE
5. Discontinuation due to AE

Tier 2 Safety Endpoints include:

1. Specific AEs, SOC AEs or PDLCs which have incidence in all 3 subjects.

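### The primary 9HPT contrast runs from V3 to V5, but the named baseline is Visit 2, stimulation starts there, and the text does not establish that V3 precedes it

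*Protocol*

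**What the plan says.** - **Endpoint.** Section 8.4.1 gives the primary endpoint as "Differences in the nine-hole peg test (9-HPT) affected hand in the tSCS treated vs. sham groups by the end of treatment (V3 vs V5". The same pair of visits stands in the synopsis (1.0), section 3.1 and Table 4. The text of 8.1 tests the treatment interaction with the 6-week follow-up and names V5, but gives no reference visit.
- **Baseline.** Table 2 (section 6.0) titles Visit 2 "Randomization Baseline", sets it at Day 42 and marks the 9HPT there. Section 7.1.5.1.2 also calls Visit 2 the baseline. Section 8.4.1 states as a general rule that efficacy measures with a baseline value are analysed as change from it, and the secondary 9HPT endpoints start from baseline.
- **Start of stimulation.** Section 7.1.5.1.2 lists randomisation, vital signs and a neurological examination at Visit 2, and continues: "Then, the patient will be subjected to the first tSCS stimulations (a 30 min stimulations". The 9HPT is not among the steps that come first.
- **V3.** Section 7.1.5.1.3 is headed "Visit 3-5: Stimulation Visits" and says that "9HPT will be assessed the last day of stimulation for each session period". The protocol does not define a session period.
- **End of treatment.** It is V5 in 8.1 and 8.4.1. The second section numbered 7.1.5.1.2 places the end of the double-blind period at Visit 13. Table 2 runs the double-blind visits to Visit 6.

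**The concern.** Taken literally, the reference value of the only primary efficacy contrast is not the protocol's baseline and is recorded at a visit where stimulation is already under way. A reference taken after randomisation and after treatment has begun can itself carry treatment effect, and subtracting it removes that part from the estimate. The primary and secondary 9HPT analyses would also start from different points.

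The order of test and stimulation on Day 42 is a matter of trial conduct, so an analysis plan written later cannot repair it. Table 2 schedules no 9HPT at screening. The entry criterion implies that a value exists by then, but it would precede the six weeks of run-in occupational therapy and could not replace a Day 42 value.

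**Working it through.** No figure in the plan is in dispute, so the check sets the dates and labels side by side.

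**1. Which day is the end of treatment?** Section 2.1 gives a 6-week run-in and then 6 weeks of randomised treatment: 42 + 42 = 84. Table 2 lists Day 84, and 8.1 speaks of a 6-week follow-up at V5. V5 = Day 84 fits all three.

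**2. Which day is V3?** Table 2 gives Visits 3 to 6 the days 42, 61 and 84.
- A six-week contrast ending on Day 84 starts at 84 − 42 = Day 42. A start at Day 61 would span 84 − 61 = 23 days, which is not six weeks.
- V3, V4 and V5 on Days 42, 61 and 84 is therefore the likely intent.
- It is not stated. Four visits have three days, so Visit 6 is left without one, and Day 42 is also the day of Visit 2.

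**3. Does V3 = Day 42 make it a pre-stimulation value?** Not by itself.
- The first stimulation is at Visit 2, also Day 42, and no section puts the 9HPT ahead of it.
- Both columns of Table 2 carry a window of ±3 days. Visit 2 on 42 − 3 = Day 39 and V3 on 42 + 3 = Day 45 are both in window, so V3 could follow the first stimulation by 45 − 39 = 6 days without a deviation.
- Section 7.1.5.1.3 points to a post-stimulation test at V3.

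**4. Other Visit 2 text.** Section 7.1.5.1.2 describes a 30-minute stimulation at Visit 2. Section 7.1.4.1 speaks of withdrawal "in the trial during visit 2 (before completing the three planned stimulations". Section 7.2.3.2 is headed "Events of Clinical Interest (during the stimulation visit 2 (in the 1h after each stimulation", and 8.4.2 says "The primary time for safety analyses is Visit 2". Section 7.1.1.9 confirms eligibility at Visit 2 but records screen failures at Visit 4. These statements do not describe one schedule.

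**5. Consequence if V3 follows stimulation.** Let D be the full tSCS-minus-sham difference in change from a pre-stimulation value to Day 84, and let fD be the part present at V3. With randomised arms equal in expectation before stimulation, the V3-to-V5 contrast estimates D − fD = (1 − f)D.
- f = 0: V3 precedes stimulation, or there is no early effect. Nothing is lost.
- 0 < f < 1: the early effect has the same sign, and the estimate is pulled toward no difference.
- f < 0: the early effect has the opposite sign, and the estimate is inflated.

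The protocol gives no value for f.

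**6. Sample size.** The power claim in 8.9 (26 per arm, difference 4.4, SD 5.5, two-sided 0.05) reproduces at 80.7% with the noncentral t distribution. It does not depend on which visit is the reference.

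**The case against.** The strongest reply is that this is a labelling problem. The dates favour V3 = Day 42, Table 2 already schedules a baseline 9HPT at Visit 2, and silence about the order is not an instruction to stimulate first. Figure 1, the trial diagram, is not shown and may define the visit labels. Much of this reply stands, and it rules out several stronger readings that a reader might infer:

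- **That V3 is shown to be post-stimulation, or was chosen as such.** It is not. The text is inconsistent, and the likelier intent is a Day 42 reference.
- **That three stimulations precede V3.** The wording in 7.1.4.1, 7.2.3.2 and 8.4.2 concerns withdrawal and safety, and it fits poorly with a 60-patient, 6-week trial. Section 8.4.2 refers to all 3 subjects, and the abbreviation list includes ALS and transcranial pulse stimulation. Carry-over from another protocol is a reasonable explanation, so these lines are weak evidence on 9HPT timing.
- **That the endpoint is biased toward no difference, with a calculable loss of power.** The direction needs an early effect of the same sign as the final one. Section 4.1.1 reports short-term gains in mobility, postural control and spasticity lasting 2 hours after a single lumbar session in MS. That makes an early effect plausible but says nothing about its size in the hand. Short-term fatigue or discomfort after a session would act the other way.

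The reply does not remove the contradiction. A site that follows 7.1.5.1.2 and 7.1.5.1.3 as written could record the reference after stimulation, and the V5, Visit 6 and Visit 13 labels cannot all mark the same point without explanation.

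**Conclusion.** This is an internal contradiction over the reference visit and end visit of the sole primary efficacy contrast. It is wrong as written, and confidence is moderate. The likely intent, Day 42 to Day 84, can be inferred from 2.1, Table 2 and 8.1, but no section states it, and the sections describing Visits 2 to 5 point elsewhere. Any bias is conditional on V3 being measured after stimulation. The estimate is then (1 − f) times the full difference, attenuated only if f is positive, and f cannot be derived from the protocol. The conclusion assumes that Figure 1, if it defines the labels, does not override the text; even then the text must agree with it. The point merits correction before enrolment because a missed pre-stimulation 9HPT cannot be recovered.

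**What to change.** 1. In the synopsis, 3.1, 8.1 with Table 4, and 8.4.1, define the primary endpoint by timing: change in 9HPT of the affected hand from the Visit 2 (Day 42) assessment, completed before the first stimulation, to the end of the 6-week double-blind period (Day 84, within window).
2. State in 7.1.5.1.2 that the Visit 2 9HPT precedes the first stimulation.
3. Reconcile Table 2, 7.1.1.9, 7.1.4.1 and 7.1.5 to one visit numbering, with a day for every visit and one label for the end of the double-blind period. Reconcile the differing descriptions of stimulation at Visit 2 as well.

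The cost is protocol wording and a line in the site instructions. The 9HPT is already scheduled at Visit 2 and in the double-blind period, so no visit or assessment is added and the sample size is unchanged.

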Measurements & Procedures	
 1. tSCS 2. Occupational Therapy 3. Clinical scales and PROs
Study Product / Intervention	tSCS is a non-invasive electric stimulation system that has shown good tolerability and signs of efficacy for improving UL disability
Controls	Sham (fictitious stimulation) will be used as control arm
Number of Participants & Rationale	
N=60 (30:30)
 
Rationale: accepting an alpha risk of 0.05 and a beta risk of 0.1 in a two-sided test, 10 subjects are necessary in each group to recognize as statistically significant a minimum difference of 10 units on the 9HPT scale between any pair of groups assuming that 2 groups exist. The common deviation is assumed to be 5.5. It has been anticipated a drop-out rate of 10%.

Study Duration:	
24 months
 
6 months recruitment, 9 months randomized phase, 6 months OLE, 3-month analysis and clinical scientific report

Timelines:	
 ● First Patient First Visit (FPFV): January 1st, 2025 ● Last Patient Last Visit (LPLV): December 30th 2026
Study Schedule:	
Patients in Spain are recruited from the three MS centers (Hospital del Mar, Hospital Clínic and Hospital Sant Pau) in Barcelona and treated in a single therapy center at Hospital del Mar located closely to all of them. Patients in the Netherlands are recruited at the Rijndam center, Erasmus Medical Center.
 
Run-in period (6 weeks with occupational therapy)
 
Double-Blinded period: 6 weeks for safety and efficacy assessments

	Open Label Extension (6 weeks) for safety and durability of efficacy
Study Center:	Hospital del Mar (HMar); Hospital Clinic of Barcelona (HCB); Hospital Sant Pau (HSP), all in Barcelona, Spain; Rijndam center, Erasmus Medical Center (EMC)
Statistical Analysis Plan	
The primary and secondary endpoints will be assessed using linear mixed-effects models (LME). These models will include the outcome measure as the dependent variable, and treatment group, time, and their interaction as independent variables, with random intercepts for participant and site to account for the longitudinal and clustered nature of the data.
 
Populations : 1) Intention to treat population; 2) Per protocol population: patients that completed 70% of the therapeutic sessions

A list of abbreviations used in this document can be found in Appendix 12.3.

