2.0 TRIAL DESIGN

2.1 Trial Design

This is a double-blinded, parallel, sham-controlled study in PwMS and with significant disability of the upper limb (UL). Participants are exposed to a 6-week run-in period with standard occupational therapy and then randomized to 6 weeks of tSCS or sham combined with ongoing occupational therapy. After completion of the double-blind period, sham-treatment participants will be offered an additional 6 weeks open-label extension (OLE) where they receive active tSCS combined with occupational therapy. Participants in the original active group will be followed with no additional stimulation or occupational therapy to assess the durability of effects. The duration of the run-in, active treatment and extended follow (6 weeks each) are defined based in the previous results from a similar therapy for SCI.

Specific procedures to be performed during the trial, as well as their prescribed times and associated visit windows, are outlined in the Trial Flow Chart - Section 6.0. Details of each procedure are provided in Section 7.0 – Trial Procedures.

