3.2 Key Secondary Objective(s) & Hypothesis(es)**Objectives:**

1. Percentage of responders: 20% difference on the 9HPTd (minimal clinically important difference (MCID)) from baseline to end of the study
2. Change in the 9HPT dominant and non-dominant hand from baseline to end of the study
3. Change in the Action Research Arm Test (ARAT) from baseline to end of the study
4. Change in the modified Ashworth Scale (mAS) for spasticity assessment from baseline to end of the study
5. Hand strength measured by Grip and Pinch force dynameters from baseline to end of the study
6. Change in the NeuroQOL Upper Extremity function from baseline to end of the study
7. Change in the Modified Fatigue Impact Scale (MFIS) from baseline to end of the study
8. Change in Global Impression of change (GIC) from baseline to end of the study

Hypothesis: Our hypothesis is that tSCS treatment of the cervical cord combined with occupational therapy is safe and efficacious for treating people with MS with moderate to severe upper limb (hands) disability. Recent multi-site clinical trials in patients with spinal cord injury (SCI) have shown excellent safety and efficacy of tSCS associated with occupational therapy to improve UL functioning (NCT04697472). Therefore, this relevant evidence support moving this therapy directly to people with MS (PwMS) with moderate to severe UL disability.

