We are using a 10 kHz overlapping frequency to apply skin-surface stimulation (Figure 3). This high-frequency waveform allows the application of 5-fold greater stimulation intensities through the skin⁶⁻⁸, which effectively reaches the spinal cord without causing discomfort^{4-7, 9}. Thus, tSCS now permits administration of effective and well-tolerated, high stimulation intensities via removable electrodes placed on the skin over the vertebrae. While our tSCS protocols are less spatially specific than implanted epidural stimulation, both activate the dorsal sensory roots as they enter the spinal cord^{3, 10-12}. Activation of sensory afferent fibers provides direct excitation of motor neurons via mono-and poly-synaptic reflexes to improve strength and function^{4-6, 9}. Stimulation likely also activates ascending sensory and other interneuron structures within the spinal cord to improve sensation and reduce spasticity without the need for surgical implantation^{5, 6}.

We have demonstrated that our method of tSCS is well-tolerated and promotes significant and meaningful recovery of upper extremity function after chronic traumatic spinal cord injury^{4, 6, 13-15}. For example, a prospective, open-label cross-over studies showed that non-invasive tSCS combined with functional task training improved upper extremity function in adults with SCI compared to functional task training alone, even after motor complete injury, and when administered up to 12 years after initial injury (Figure 4)⁴.

[figure not shown]

Figure 4: Stimulation improved hand and arm function, which was sustained for 3-6 months in participants with cervical spinal cord injury. All six participants improved hand function during transcutaneous stimulation paired with training. Stimulation combined with training led to greater improvements than training alone in bilateral (A) pinch force, (B) Graded Redefined Assessment of Strength, Sensation and Prehension (GRASSP test), and (C) GRASSP quantitative prehension. Improvements that occurred during stimulation paired with training were maintained for at least 3 to 6 months of follow-up. *: $p < 0.05$; NS: $p > 0.05$.

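### The secondary efficacy endpoints are measured to the end of the study, a visit that falls after sham participants have been offered active tSCS

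*Protocol*

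**What the plan says.** The synopsis (Section 1.0) and Section 3.2 list eight secondary efficacy endpoints, all running from baseline to the end of the study. Table 4 and Section 8.4.1 repeat the list. The responder endpoint is typical: "Percentage of responders: 20% difference on the 9HPTd (minimal clinically important difference (MCID)) from baseline to end of the study". Grip and pinch strength is the one exception. Section 3.2 has "Hand strength measured by Grip and Pinch force dynameters from baseline to end of the study", but Table 4 and Section 8.4.1 replace the window with a figure reference.

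The primary endpoint, in the same lists, is worded differently. It compares the 9HPT of the "affected hand in the tSCS treated vs. sham groups by the end of treatment (V3 vs V5").

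Section 5.10 ends the trial at the last study-related call or visit. In the flow chart (Section 6.0) the last visit is Visit 7, labelled OLE, on Day 126, and the 9HPT, ARAT, mAS, NeuroQOL, MFIS and GIC are all marked there.

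Section 2.1 describes what happens between Day 84 and Day 126. For one arm, "sham-treatment participants will be offered an additional 6 weeks open-label extension (OLE) where they receive active tSCS combined with occupational therapy". For the other, "Participants in the original active group will be followed with no additional stimulation or occupational therapy to assess the durability of effects".

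Section 8.1 tests treatment arm on all primary and secondary endpoints with a mixed model containing arm, time and their interaction. It names the 6-week interaction as the test for the primary outcome only and classes every other time point and outcome as secondary.

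**The concern.** Two different phrases, used side by side in every efficacy list, naturally mean two different time points. Read as written, the secondary window closes after the randomised comparison has been taken apart. The sham arm has crossed to active treatment to whatever extent its members accept the offer, and the active arm has stopped both stimulation and therapy. The arm contrast then compares delayed tSCS with earlier tSCS followed by a treatment-free period.

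The contrast is also open, because only sham participants are offered stimulation in the OLE, so the offer itself reveals allocation. That matters most for NeuroQOL, MFIS and GIC, which rest on the patient's own report.

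Section 4.1.1 says this pilot is to inform the design of pivotal trials. A diluted responder rate or ARAT difference would misinform that step. And because the design points to Day 84 while the endpoint wording points to Day 126, the time point could be settled after the data are seen.

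**Working it through.** **Timing.** The flow chart puts randomisation and baseline at Day 42. Day 42 + 6 weeks (42 days) = Day 84, the end of the double-blind period. Day 84 + 6 weeks = Day 126, the OLE visit. The literal window is therefore Day 42 to Day 126, not Day 42 to Day 84.

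**State of each arm at the two visits (Section 2.1)**

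| Visit | Assigned tSCS | Assigned sham |
|---|---|---|
| Day 84 | 6 weeks of tSCS + therapy | 6 weeks of sham + therapy |
| Day 126 | then 6 weeks of neither | then 6 weeks of open-label tSCS + therapy, in those who accept |

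Only the Day 84 row isolates stimulation.

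**The plan's own figure.** Inputs from Section 8.9: standardised effect 0.8, SD 5.5, 26 per arm, two-sided alpha 0.05.

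- Difference = 0.8 × 5.5 = 4.4 units.
- Noncentrality = 4.4 / (5.5 × √(2/26)) = 2.884; critical t on 50 df = 2.009.
- Power = 80.7%, which agrees with the stated figure of more than 80%.

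**Illustration at Day 126.** Let r be the share of the Day 84 effect that the active arm retains, and u the share of sham participants who take the OLE. Assume each taker gains the same 4.4 units. Then

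Day 126 difference = 4.4 × (r − u).

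| r | u | Difference | Two-sided power |
|---|---|---|---|
| 1.0 | 0.5 | 4.4 × 0.5 = 2.20 | 29.3% |
| 1.0 | 0.8 | 4.4 × 0.2 = 0.88 | 8.7% |
| 1.0 | 1.0 | 0 | 5.0% |
| 0.5 | 0.5 | 0 | 5.0% |
| 0.5 | 0.8 | 4.4 × (−0.3) = −1.32 | 13.6% (13.3% favouring the sham-assigned arm) |
| 0.5 | 1.0 | 4.4 × (−0.5) = −2.20 | 29.3% (nearly all favouring the sham-assigned arm) |

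Partial uptake also widens the spread in the sham arm, adding 4.4² × u(1 − u) to its variance. The pooled SD becomes √((5.5² + 5.5² + 4.84)/2) = 5.72 at u = 0.5, and √((5.5² + 5.5² + 3.10)/2) = 5.64 at u = 0.8. Power in the r = 1.0 rows then falls slightly, to 27.5% and 8.6%.

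**Which rows are more plausible.** Section 4.1.1 reports, for six people with spinal cord injury, that "Improvements that occurred during stimulation paired with training were maintained for at least 3 to 6 months of follow-up". If that carries over to MS, r is near 1 and the result is dilution. Reversal needs r < u, so it needs the active arm to lose benefit.

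The document gives no effect size or SD from which to repeat this for ARAT, mAS, NeuroQOL, MFIS, GIC or the responder rate.

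**The case against.** The strongest reply is that the design makes the intention clear. The synopsis assigns efficacy assessment to the double-blind period and describes the extension as "Open Label Extension (6 weeks) for safety and durability of efficacy". The mixed model has an arm-by-time term, so it can deliver a Day 84 contrast for every outcome measured then, and Section 8.1 does not exclude it. Section 8.4 speaks of evaluation within and/or between protocols, which leaves room for a within-arm reading of Day 126. Which contrast is reported for each secondary outcome is often left to an SAP.

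This makes a Day 84 intention plausible, but it does not remove the problem. The synopsis sentence describes periods, not endpoints. Section 8.1 picks the 6-week contrast for the primary outcome alone. The finding does not rest on missing detail: the protocol states a window, repeats it in four places, and that window does not suit a between-arm test. An SAP that chose Day 84 would contradict the protocol.

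Some points on the other side do stand:

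- The power figures are illustrative. Section 8.9 powers only the primary endpoint, so no planned secondary power is being lost.
- The synopsis sample-size rationale uses 10 units with the same SD rather than 4.4. The proportional dilution is the same, but the absolute figures would differ.
- The durability data are the only multi-week data in the text available for review. Some of the preliminary-results pages are not in it.
- The protocol does not say whether Day 126 raters are separate from treating staff, so the loss of blinding is certain only for those who know who was offered the OLE.
- A clearly labelled early-versus-delayed comparison at Day 126 would also be legitimate. It would simply not be tSCS versus sham.

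**Conclusion.** The concern holds: the secondary endpoint window is wrong as written. All eight secondary efficacy endpoints are affected in the synopsis and Section 3.2, and seven of eight in Table 4 and Section 8.4.1, where grip and pinch has no window at all. The primary endpoint is not affected.

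The fault in the contrast follows from Sections 2.1, 5.10 and 6.0 and needs no assumption beyond some sham participants accepting the offer. Its size does depend on assumptions about uptake, retention and an equal gain in the OLE. Under full retention, the 9HPT difference shrinks in direct proportion to uptake and vanishes at 100%. For the other outcomes the direction is the same, but the size cannot be computed from the document. This should be corrected before the analysis, although it does not threaten the main conclusion of the trial.

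**What to change.** 1. Reconcile the visit numbers first. The primary endpoint uses V3 and V5. The flow chart spreads Visits 3-6 over three days (42, 61 and 84). Section 7.1.5 uses Visits 13, 14 and 29 for the end of the double-blind period and the start and end of the OLE. It also places the first stimulation at Visit 2, so the baseline measurement must be stated to precede it.
2. In the synopsis, Section 3.2, Table 4 and Section 8.4.1, define each between-arm secondary endpoint from that pre-stimulation baseline (Day 42) to the end of the double-blind period (Day 84), the same window as the primary endpoint.
3. In Section 8.1, state that the arm-by-time contrast at that visit is the test for each secondary endpoint.
4. Give grip and pinch strength the same window in Table 4 and Section 8.4.1, and add a row for it to the flow chart, where it is absent.
5. Report Day 126 within arm: durability in the original active arm, and open-label response in sham participants who enter the OLE. If an early-versus-delayed comparison is wanted as well, label it as such.

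The cost is wording in four lists and Section 8.1, consistent visit numbers and one flow-chart row. No visits or participants are added, because the other six measures are already scheduled at the double-blind visits.
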